## 8. Study Assessments and Procedures

- Study procedures and their timing are summarized in the SoA. Protocol waivers or exemptions are not allowed.
- Immediate safety concerns should be discussed with the sponsor immediately upon occurrence or awareness to determine if the participant should continue or discontinue study intervention.
- Adherence to the study design requirements, including those specified in the SoA, is essential and required for study conduct.
- All screening evaluations must be completed and reviewed to confirm that potential participants meet all eligibility criteria. The investigator will maintain a screening log to record details of all participants screened and to confirm eligibility or record reasons for screening failure, as applicable.

### 8.1. Safety Assessments

Planned time points for all safety assessments are provided in the SoA.

#### 8.1.1. Physical Examinations

- Assessment of pain levels
- Assessment of experience during and after anesthesia
- Cognitive assessments using CANTAB IPAD software

### 8.2. Adverse Events(AE) and Serious Adverse Events(SAE)

There will be a collection of data on adverse events; movement during surgery, serious hypotension during anesthesia (MAP<60) or awareness with recall after surgery, and other events that is related to the anesthetic administration. We will not collect data on events related to the surgery.

#### 8.2.1. Time Period and Frequency for Collecting AE and SAE Information

Data on adverse events will be collected directly after surgery, and on the 2 postoperative visits.

#### 8.2.2. Follow-up of AEs and SAEs

All SAEs, and AEs of special interest will be followed up until resolution, or the event is otherwise explained, or the participant is lost to follow-up.

### **8.2.3. Regulatory Reporting Requirements for SAEs**

- The only unexpected and Serious Adverse Event in our planned study, will be the occurrence of awareness with recall after surgery.
- Prompt notification by the investigator to the sponsor of a SAE is essential so that legal obligations and ethical responsibilities towards the safety of participants and the safety of a study intervention under clinical investigation are met.
- The sponsor has a legal responsibility to notify both the local regulatory authority and other regulatory agencies about the safety of a study intervention under clinical investigation. The sponsor will comply with country-specific regulatory requirements relating to safety reporting to the regulatory authority, Institutional Review Boards (IRB)/Independent Ethics Committees (IEC), and investigators.

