### **2.3. Benefit/Risk Assessment**

The benefit for the participants in this study is an increased attention from the anesthetic staff, and that the monitoring of levels of anesthesia will be standardized and thorough regardless of which study-group you wind up in. The risk of awareness during surgery is what we always achieve to avoid, and the risk of this is low in both study-arms. We will screen for this after surgery; all patients will be interviewed to assess their experience of the procedure, what they remember and overall satisfaction with our treatment.

Both arms of the study represents ways of delivering general anesthesia in surgery today. The incidence of awareness in North America and Europe is 1 to 2 cases/1000 (45-50). A 2019 meta-analysis of randomized trials compared BIS-EEG guidance of anesthetic depth to reduce the risk of awareness from 9 to 3 pr 1000 (51). So there is a small possibility that the intervention reduces the risk for awareness for the participants in this study.

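### Section 8.2.3 closes the SAE category to awareness with recall, no seriousness criteria reopen it, and the label unexpected conflicts with 2.3 and 8.2

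*Protocol*

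**What the plan says.** Section 8.2.3 of the protocol opens with: "The only unexpected and Serious Adverse Event in our planned study, will be the occurrence of awareness with recall after surgery". Its next bullet ties the investigator's duty towards the sponsor to that label: "Prompt notification by the investigator to the sponsor of a SAE is essential".

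Section 8.2.2 sets the follow-up rule: "All SAEs, and AEs of special interest will be followed up until resolution, or the event is otherwise explained". Loss to follow-up also ends it. The AEs of special interest are not listed there or anywhere else.

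Section 8.2 collects a wider set of events. It names "movement during surgery, serious hypotension during anesthesia (MAP<60) or awareness with recall after surgery" and then leaves the list open: "and other events that is related to the anesthetic administration". Surgery-related events are deliberately left out, which is a separate choice and not at issue here.

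Section 2.3 treats awareness as a known risk. It gives an incidence of 1 to 2 per 1000 in North America and Europe, cites a meta-analysis in which the risk was 9 versus 3 per 1000, and commits to interviewing all patients after surgery.

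Appendix 2 defines an AE and describes recording, causality assessment and follow-up of AEs. It has no SAE definition, and the table of contents lists none.

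**The concern.** Whether an event is serious should be decided when it occurs, from its consequences. Section 8.2.3 instead names one event in advance and words it as the only one. An anesthetic-related death, cardiac arrest or anaphylaxis would be collected as an AE under the open-ended part of 8.2. Read literally, 8.2.3 would not make it an SAE.

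Two things hang on that label: prompt notification of the sponsor, and follow-up until resolution. The label also decides which events appear in the SAE count for each arm. If only awareness can be an SAE, the comparison of serious harm between arms reduces to a comparison of awareness.

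The word unexpected is a second problem. An event with a quoted incidence, a planned interview to detect it and a place on the list of events to collect is anticipated by the protocol's own account.

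**Working it through.** The protocol states no figure on this point to reproduce. The check is mainly a comparison of sections, with a short calculation for scale.

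**1. Does any text reopen the SAE category?** Sections 8.2 to 8.2.3 contain no seriousness criteria. In Appendix 2, 10.2.1 defines an AE and 10.2.2 covers recording, causality and follow-up of AEs. The causality text calls causality one of several criteria for regulatory reporting but gives no rule for seriousness or expectedness. The table of contents shows only those two entries under Appendix 2, so the absence does not come from removed pages. The first bullet of 8.2.3 is the only sentence that says what an SAE is.

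**2. Which duties reach a serious anesthetic-related event other than awareness, read as written?**

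- *Prompt notification of the sponsor (8.2.3):* triggered by the SAE label, so not triggered.
- *Follow-up until resolution (8.2.2):* triggered by the SAE label or by being an AE of special interest. The first does not apply; the second cannot be determined, because no list exists.
- *Urgent safety concerns taken to the sponsor (section 8):* independent of the label, so it can apply. Its stated purpose is to decide whether the participant continues the intervention, which fits poorly once anesthesia is over.
- *Notification of the IRB/IEC (10.1.1):* extends beyond SAEs to other important safety findings, so it can apply, but the recipient is not the sponsor.
- *Recording, causality assessment and further evaluation (10.2.2):* applies to every AE. It includes no seriousness classification and does not say how long follow-up lasts.

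The event would be recorded and evaluated, and might reach the sponsor or the IRB/IEC. It would not be classified as serious, and neither SAE-specific duty would clearly apply.

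**3. Expectedness.** Section 2.3 quotes rates and plans an interview of every patient; 8.2 names awareness with recall among the events to collect; 8.2.3 calls it unexpected. The first two do not fit the third.

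**4. Scale.** Inputs: 100 participants, 50 per arm (section 9.2); awareness rates from section 2.3. With independent participants, the chance of no case among n at rate p is (1 − p)^n.

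- p = 0.001: expected 100 × 0.001 = 0.1; chance of none 0.999^100 = 0.905.
- p = 0.002: expected 100 × 0.002 = 0.2; chance of none 0.998^100 = 0.819.
- 9 per 1000 in one arm and 3 per 1000 in the other: expected 50 × 0.009 + 50 × 0.003 = 0.45 + 0.15 = 0.6; chance of none 0.991^50 × 0.997^50 = 0.636 × 0.861 = 0.548.

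Under the literal rule, these are the chances that the trial records no SAE, whatever other serious anesthetic-related events occur.

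**The case against.** The strongest reply is that the sentence need not be read as closing the category. It can mean the only event that is both unexpected and serious, or it can be a forecast. Other text suits an open category: 8.2.2 speaks of SAEs in the plural, the remaining bullets of 8.2.3 are general, and 10.2.2 has each AE assessed for causality individually. This stands as a point about ambiguity. It does not remove the problem, because under either alternative the investigator still has no rule for deciding whether another event is serious, and unexpected still conflicts with 2.3.

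Several stronger conclusions that a reader might draw are not supported:

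- *That other serious events would go unnotified and without follow-up.* Sections 8, 10.1.1 and 10.2.2 provide the partial routes set out above. What is missing is the SAE-specific duty, not all handling.
- *That 8.2 directly contradicts 8.2.3 over hypotension.* Section 8.2 calls MAP below 60 serious hypotension but does not class it as an SAE; the word may mean severe. This is a tension to clarify.
- *That the label sends awareness down a wrong reporting route.* The protocol describes no separate routes for expected and unexpected events.
- *That the trial would report no SAEs by definition.* Awareness would count, and it is actively looked for. The 82% to 90% chance of none holds only at the lower rates in 2.3.

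Serious anesthetic-related events could also be identified later from the AE records, since these are collected in both arms. That limits the damage but leaves the classification to be made retrospectively.

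**Conclusion.** The point holds in a limited form. Section 8.2.3 words the SAE category as closed to awareness with recall, and nothing else in the protocol says what makes an event serious. As written, other serious anesthetic-related events fall outside the SAE notification duty and the SAE follow-up rule and would not be counted as serious in either arm, although other sections cover them in part. The label unexpected is inconsistent with 2.3 and 8.2.

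The figures show scale only. The chance of a zero SAE count is about 82% to 90% at the background rate and about 55% at the meta-analysis rates. Both depend on the literal reading, on 100 participants, and on the rates in 2.3 applying to these patients. This is stated text that misclassifies events rather than detail that could be left to an SAP, and it warrants an amendment because safety reporting rests on it. No endpoint, power or alpha is affected.

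**What to change.** - Replace the first bullet of 8.2.3 with a general SAE definition based on outcome (for example death, threat to life, prolonged hospital stay, lasting disability), applied to each event as it occurs.
- Keep awareness with recall as an event that is always reported as an SAE, and delete *only*.
- Reconcile the label *unexpected* with 2.3 and 8.2.
- Clarify in 8.2 whether *serious* hypotension means severe or is meant as an SAE.
- Have the sponsor state which events are the AEs of special interest in 8.2.2. The protocol does not show which were intended, so the list should not be inferred from 8.2.
- Add a seriousness field to the AE CRF page.

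The cost is a short amendment to 8.2 to 8.2.3, one CRF field, and possibly a few more events needing prompt reporting.

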## 9. Statistical Considerations

### 9.1. Statistical Hypotheses

We anticipate that wake-up happens at mean 15 min, standard deviation 5 min (41-44) in the control group. We hypothesize that there will be an improvement of 20% (3 min) in the intervention group.

### 9.2. Sample Size Determination

We hypothesize that the intervention will reduce amount of propofol administered by up to 20%, also that wake-up may be reduced from 15 min, SD 5 min – to 20 min SD 3 min. With an improvement of 20%, 80% power and a significance level of 0.05, the study will require 88 patients in total, calculated in a two-sample t-test. To add for margin of error/loss we will include 50 patients in each group, summing at 100 patients in total. Due to a difference in plasma levels of anesthetic drugs in men and women, we will do gender stratification when randomizing, to ensure an equal number of sexes in both groups.

### 9.3. Populations for Analyses

The following populations are defined:

Population	Description
Enrolled	All participants who sign the ICF
Randomly Assigned to Study Intervention	50-50
Evaluable	All

### 9.4. Statistical Analyses

The statistical analysis plan will be finalized prior to database lock, and it will include a more technical and detailed description of the statistical analyses described in this section. This section is a summary of the planned statistical analyses of the most important endpoints including primary and key secondary endpoints.

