### Overall Design

**Disclosure Statement:** This is an interventional study. The study has two arms, and is single blinded for the participant, and assessment masked for the investigator. It is blinded for the post-operative care providers.

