### 3. Objectives and Endpoints

Objectives	Endpoints
Primary	

• Use of DoA-mon reduces anesthetic dosage and wake-up times

	

• Total amount of propofol (mg/kg/hr) administered

• Time to wake-up after stop of anesthetic administration

Secondary	

• Use of DoA-mon reduces POCD

	

• Cognitive functioning

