### 4.1. Overall Design

Both groups will receive standard of care in total intravenous anesthesia (TIVA), with monitoring of clinical signs relating to level of anesthesia and to the satisfaction of the surgeon. In the intervention group, the anesthesia providers will guide the dosage of hypnotics based on a BIS-index of 45-60 perioperative, also avoiding burst-suppression (visually detected)/suppression-ratio (SR) of 0, and EEG-frequency alpha (peak alpha) of 10-12 hz.

All patients will have a recording of their perioperative EEG. All patients will be assessed pre and postoperatively using the Cambridge Neuropsychological Automated Test Battery (CANTAB) to assess how they are affected, testing for executive cognitive functioning. The participants use an IPAD to self-assess, so the assessor is blinded.

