#### 9.4.1. General considerations

#### 9.4.2. Primary endpoint(s)

Medication usage; total amount of propofol used (mg/kg/hr) from start to end of anesthesia.

TCI effect site target at start, and each 10 min interval during anesthesia.

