#### **10.1.4. Data Protection**

- Participants will be assigned a unique identifier by the sponsor.
- The participant must be informed that his/her personal study-related data will be used by the sponsor in accordance with local data protection law. The level of disclosure must also be explained to the participant who will be required to give consent for their data to be used as described in the informed consent
- Third party software providers (Cambridge Cognition), will store data from the CANTAB cognitive assessment tests as without name or information which would make the participant identifiable. These results will be stored on extra safe servers belonging to Cambridge Cognition in the UK, accessed only by principal investigator and PhD-fellow in the study-group. The handling of this data is covered in the DAP agreement between sponsor, and Cambridge Cognition.

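### The SAP need only be final before database lock, although dosing is open and the protocol's lists disagree on which endpoints beside propofol are primary

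*Protocol*

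**What the plan says.** **Timing of the SAP.** Protocol section 9.4: "The statistical analysis plan will be finalized prior to database lock". The same sentence limits its role: "it will include a more technical and detailed description of the statistical analyses described in this section". No section sets an earlier date or links the date to who has seen data by arm.

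**Who knows the arm.** In the intervention group, section 4.1 says "the anesthesia providers will guide the dosage of hypnotics based on a BIS-index of 45-60 perioperative". Under section 6.2 the EEG display is covered in controls only, so the dosing staff know the allocation by design. The synopsis calls the trial "single blinded for the participant, and assessment masked for the investigator". Section 6.2 explains the investigator's masking through patients testing their own cognition on a tablet. It also says that the anesthesia providers do not assess outcome and that an outside party randomizes.

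**Who can see data.** CANTAB results are "accessed only by principal investigator and PhD-fellow in the study-group" (section 10.1.4). The investigator verifies and signs the case report form (section 10.1.7).

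**Primary endpoint.** Section 3, like the synopsis, lists two: "Total amount of propofol (mg/kg/hr) administered" and "Time to wake-up after stop of anesthetic administration". Section 9.4.2 lists "Medication usage; total amount of propofol used (mg/kg/hr) from start to end of anesthesia" and the TCI effect-site target at the start and every 10 minutes. Section 9.4.3 places time to wake-up among the secondary endpoints, with extubation, verbal response and motor response as end events.

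**The concern.** A deadline at database lock protects the analysis when those who write the plan cannot see outcomes by arm. Here the dosing staff generate the propofol and TCI data while knowing the arm. The investigator masking that section 6.2 describes concerns cognition, not dosing or wake-up. No rule separates the authors of the SAP from propofol, TCI or wake-up data by arm.

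This matters because the protocol itself disagrees about what is primary. Someone has to resolve that before the analysis, and section 9.4 as worded allows it after about 100 patients' data exist. If the resolution were informed by results by arm, the 0.05 significance level in section 9.2 would no longer describe the chance of a false-positive conclusion.

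**Working it through.** **1. Which endpoint the sample size belongs to.** Inputs from section 9.1: control mean 15 min, SD 5 min, improvement 3 min. From section 9.2: 80% power, significance level 0.05, two-sample t-test, 88 patients. Two-sided testing and a common SD of 5 are assumed. (Section 9.2 prints 20 min, SD 3, for the wake-up time after reduction. That is not a reduction from 15 min, so the 3 min of section 9.1 is used.)

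n per arm = 2 × (1.960 + 0.842)² × 5² / 3² = 2 × 7.85 × 25 / 9 = 43.6, rounded up to 44, so 88 in total.

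This reproduces the stated figure. The exact t-test gives 44.59, so 45 per arm and 90 in total. With 50 per arm, power is 85.1% (normal approximation) or 84.4% (t-test). The sample size is thus derived from wake-up time, which section 9.4.3 calls secondary.

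**2. The lists side by side.**

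| Measure | Sections 1.1 and 3 | Sections 9.4.2 and 9.4.3 | Sections 9.1 and 9.2 |
|---|---|---|---|
| Propofol, mg/kg/hr | primary | primary | up to 20% reduction hypothesized; no SD given |
| Wake-up time | primary, end event not named | secondary, three end events | basis of the 88 |
| TCI target series | not listed | primary, no summary measure | not mentioned |

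Propofol is fixed. Open are whether wake-up time is also primary, whether the TCI series is also primary, and which wake-up end event counts.

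**3. What an informed choice would cost.** Assume no true effect, k candidate measures each tested two-sided at 0.05, and the most favourable one taken as the lead. With independent measures the false-positive chance is 1 − 0.95^k:

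- k = 2: 1 − 0.9025 = 9.75%
- k = 3: 1 − 0.8574 = 14.3%
- k = 5: 1 − 0.7738 = 22.6%

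With a common correlation between the test statistics, simulation (400,000 draws) gives:

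| Candidates | Independent | Correlation 0.5 | Correlation 0.9 |
|---|---|---|---|
| 2 (propofol, one wake-up time) | 9.75% | 9.1% | 7.1% |
| 3 (plus the TCI target) | 14.3% | 12.6% | 8.3% |
| 5 (wake-up split into its three end events) | 22.6% | 18.2% | 10.2% |

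The correlations are assumptions; the protocol gives none. Over these settings the range is about 7% to 23%. The calculation also assumes that one significant result is enough. If all primaries had to succeed, this inflation would not arise.

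**The case against.** The strongest reply is that the quoted sentence is ordinary. Many trials finalize the SAP before lock, and the sentence states nothing false. Section 9.4 also confines the SAP to detailing analyses already listed, so it does not invite a new choice of endpoint. Both points stand. The deadline is a weakness only in combination with open dosing and endpoint lists that disagree.

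A reader might infer that the investigators can read outcomes by arm throughout the trial. The documents do not say so. Section 10.1.4 restricts who may open CANTAB results, gives no timing and no link to arm, and concerns a secondary endpoint stored without identifying information. Signing the case report form implies sight of dosing and wake-up data, but again not by arm. The protocol does not say who holds the allocation list, who writes the SAP, or whether the investigators also give the anesthetics. What remains is that nothing prevents such access.

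A reader might also infer that the primary measure is wholly open. It is not, because propofol in mg/kg/hr is primary in every list. Five candidates is therefore an upper count, and three of the five are end events that section 9.4.3 labels secondary.

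Finally, closing CANTAB alone would protect none of the measures in the calculation.

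**Conclusion.** The point holds as a cheap improvement, not as an error in the quoted sentence. The protocol lets the status of wake-up time and of the TCI series, and the choice of wake-up end event, be settled after data exist. It has no safeguard that keeps those who settle them from data by arm. The documents do not show that anyone has such access or would use it.

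The size is conditional. With two candidates the 5% error would become about 7% to 10%, and with five about 10% to 23%. This assumes correlations from 0 to 0.9, a choice informed by results, and one success being enough. The underlying cause is the contradiction between the endpoint lists; the late date only allows it to be resolved too late. An earlier SAP alone would leave the protocol listing wake-up time as both primary and secondary. The SAP was not available, so whether it was in fact signed early is unknown.

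**What to change.** 1. **Reconcile the primary endpoint by amendment.** Make sections 1.1, 3, 9.4.2 and 9.4.3 agree on whether wake-up time and the TCI series are primary beside propofol. Name the one end event that defines wake-up. If the TCI series stays primary, name its summary measure. State which endpoint the sample size in section 9.2 serves, and whether one or all primaries must succeed.

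2. **Replace the timing sentence in section 9.4**, for example: *The statistical analysis plan will be signed and dated before the first participant is randomised, or at the latest before anyone who writes it has seen propofol, TCI, wake-up or CANTAB data by arm.* The fallback must refer to those who write the plan, because dosing staff see their own patients' data by arm from the first case.

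Cost: the same document written earlier, and one amendment, which section 10.1.1 sends to the ethics committee for approval. The sample size and data collection do not change on account of the timing rule.
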